9.3. Cohorts for Analyses

The following study cohorts will be evaluated.

9.3.1. All screened Set

The all screened set will include all screened patients.

9.3.2. All Enrolled Set

The all enrolled set will include all successfully screened subjects in the study.

9.3.3. Full Analysis Set

The Full Analysis Set (FAS) will include all enrolled patients except for those who discontinued the study during Visit 1.

Study objectives will be assessed on the FAS. The population set for each analysis will change according to the subjects evaluable for the specific endpoint.

Note: Subjects using antibiotics on a continual basis (defined as more than 1 month in total) will be allowed to continue study participation, but may be eliminated from the analyses.

9.4. Analysis of demographics

Demographic characteristics (age at enrolment, gender and geographical ancestry) and cohort description will be summarised using descriptive statistics:

- Frequency tables will be generated for categorical variable such as geographical ancestry.
- Mean, median, standard deviation, minimum and maximum will be provided for continuous data such as age.

The distribution of subjects enrolled among the study sites will be tabulated.

Withdrawal status will be summarised according to the reason for withdrawal. The number of withdrawn patients will be tabulated by study visit and overall.

All tables will also be generated by country.

9.5. Analysis of primary objective

The proportion of sputum samples obtained at each visit (confirmed stable visits* and AECOPD visits and positive for specific bacterial/ viral pathogens by bacteriological methods and PCR, respectively (overall and by bacterial/viral species) will be computed with 95% confidence intervals.

* A confirmed stable visit will be defined as a scheduled study visit for which the investigator confirms in the eCRF that the subject is stable/ has recovered from a previous exacerbation.

9.6. Analysis of secondary objectives

The proportion of sputum samples obtained at each visit (confirmed stable visits* and AECOPD visits [any severity, mild, moderate and severe]) and positive for specific bacterial pathogens by both bacteriological methods and PCR (overall and by bacterial species) will be computed with 95% confidence intervals.

** A confirmed stable visit will be defined as a scheduled study visit for which the investigator confirms in the eCRF that the subject is stable / has recovered from a previous exacerbation.*

The proportion of sputum samples obtained at each stable visit and positive for specific bacterial/viral pathogens by bacteriological methods and PCR, respectively (overall and by bacterial/ viral species) will be computed with 95% confidence intervals, by GOLD grade at enrolment.

The proportion of sputum samples obtained at each AECOPD visits and positive for specific bacterial/ viral pathogens by bacteriological methods and PCR, respectively (overall and by bacterial/viral species) will be computed with 95% confidence intervals, by AECOPD severity.

The proportion of sputum samples obtained at each confirmed stable/AECOPD visit with previous administration of antibiotics or not and positive for specific bacterial/ viral pathogens by bacteriological culture and PCR, respectively (overall and by bacterial/viral species) will be computed with 95% confidence intervals.

The following incidence rates will be computed, with 95% confidence intervals (CI):

- All-cause AECOPD.
- AECOPD having sputum containing bacterial pathogens found by PCR *or* by bacteriological methods or by both methods (overall and by, but not limited to, the following bacterial species: *H. influenzae*, *M. catarrhalis*, *S. pneumoniae*, *S. aureus*, and *P. aeruginosa*).

The 95% CI of the incidence rate will be computed using a model which accounts for repeated events. The Generalised linear model assuming the Negative Binomial distribution for the response variable with logarithm as link function, and the logarithm of time for follow-up as an offset variable will be used. The incidence rates described above will also be computed for mild, moderate severe AECOPD and by GOLD grade at enrolment and will be estimated by country.

The number of subjects that report at least 1 AECOPD will be tabulated and descriptive statistics (median, mean, range, standard deviation, first and third quartiles) on the number of days of AECOPD episodes will be presented, for any, mild, moderate and severe AECOPD.

Descriptive statistics (median, mean, range, standard deviation, first and third quartiles) on the CAT and SGRQ-C scores will be tabulated at each respective visit.

Summary statistics (mean, median, standard deviation, maximum and minimum) on post-bronchodilator FEV1% of predicted normal value will be tabulated at each respective visit.

Descriptive summaries on healthcare use will be provided.

9.7. Analysis of tertiary objectives

Descriptive statistics (median, mean, range, standard deviation, first and third quartiles) on the end date of AECOPD as provided by the investigator or estimated by EXACT-PRO (via a specific algorithm which will be detailed in the Statistical Analysis Plan) will be presented.

Descriptive summaries of the quantity of specific bacteria at each scheduled [stable] and exacerbation visit will be provided for both culture and PCR analysis.

Descriptive summaries of the quantity of specific viruses at each scheduled [stable] and exacerbation visit will be provided for PCR analysis.

A conditional logistic model will be fitted to estimate the odds ratio of being in a stable state vs. an exacerbation state given the presence or not of several bacterial pathogens found by bacteriological culture and by country. The same model will also be performed for bacterial and viral pathogens found by PCR.

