1.2. Rationale for the study

Because the infectious aetiology of AECOPD has been suggested to vary according to geographical region, the primary purpose of this study (which will be conducted in several countries in Asia Pacific) is to evaluate the occurrence of potential bacterial and viral pathogens in the sputum of stable COPD patients and at the time of AECOPD. Given the increasing and projected burden of COPD in the Asia Pacific region, this study will also evaluate the frequency, severity and duration of AECOPD, as well as the impact of AECOPD on health-related quality of life (HRQOL), healthcare utilisation and lung function.

In addition, both PCR and bacteriological methods will be used for characterisation and (quantification in some cases) of bacteria in sputum. To date, identification of bacteria and assessment of bacterial load is done in the vast majority of cases by culture. However, the few studies that have compared culture with PCR demonstrated that PCR is more discriminatory at detecting typical airway bacteria [Curran, 2007; Singh, 2014]. Moreover, in a multi-centre study, PCR has the advantage that it can be performed on stored sputum samples, and can therefore be done centrally, whereas culture has to be performed on fresh sputum samples, which can lead to variable results due to variability in testing methods between laboratories.

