6.4.4. Impact of occurrence of bacterial/viral pathogens in sputum on AECOPD

The following proportions and 95% CIs will be computed:

- Proportion of sputum samples which are positive for specific pathogens [NTHi, Mcat, S. pneumoniaeP. aeruginosa, K. pneumoniae, HRV] at an AECOPD visit but not at the previous stable visit and proportion of sputum samples which are positive for specific pathogens [NTHi, Mcat, S. pneumoniae, P. aeruginosa, K. pneumoniae, HRV] at an AECOPD visit but not at the previous visit (either stable or AECOPD visit) (apparition).

Proportion of sputum samples which are positive for specific pathogens [NTHi, Mcat, S. pneumoniae, P. aeruginosa, K. pneumoniae, HRV] which appeared for the first time, during the study, at an AECOPD visit (acquisition). For both acquisition and apparition, the CIs will be estimated using a GEE model assuming a binomial distribution for the response variable with logit as link function and a compound symmetry correlation matrix (exchangeable structure) to account for the within-patient correlation.

In addition to these proportions the following odds ratios (ORs) will be calculated:

- Odds of experiencing an AECOPD (vs. being in a stable state) for patients with sputum positive for selected pathogens (vs. those with negative sputum)
- Odds of experiencing an AECOPD (vs. being in a stable state) for patients with sputum positive for selected pathogens for the first time during the study (acquisition) vs. those without acquisition
- Odds of experiencing an AECOPD (vs. being in a stable state) for patients with sputum positive for selected pathogens which was negative at the previous visit (apparition) vs. those without apparition

To obtain the odds ratios conditional logistic regression models, stratified by patient, will be fitted. Separate analyses considering bacteria detected by culture and PCR as well as viruses detected by PCR will be conducted. For each analysis, three models will be run: the first will include the pathogen, season and the interaction term between the pathogen and season, the second will include the pathogen and will be adjusted for season (without the interaction term) and the third will only include the pathogen. Season will be treated as a dichotomous variable with high season (October to March) and low season (April to September)..

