The conditional logistic model allows estimating the impact of independent variables from observations from each individual patient. In other words, by stratifying by patient, there is no need to adjust for time-invariant covariates such as age and sex.

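### Protocol 9.7 plans the stable-versus-AECOPD odds ratios by country, but SAP 6.4.4 produces only odds ratios pooled over countries and SAP section 9 records no change

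*Protocol*

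**What the plan says.** Protocol 9.7 plans a conditional logistic model that contrasts stable with AECOPD samples, with the odds ratio to be obtained "given the presence or not of several bacterial pathogens found by bacteriological culture and by country". It is to be repeated for bacteria and viruses detected by PCR. The section names neither the stratum nor the form in which country enters.

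SAP 6.4.4 (Amendment 2, current) supplies the stratum: "To obtain the odds ratios conditional logistic regression models, stratified by patient, will be fitted". It defines the odds the other way round, as AECOPD against stable. It then fixes the terms: "For each analysis, three models will be run: the first will include the pathogen, season and the interaction term between the pathogen and season". Another model drops the interaction, and the last keeps the pathogen alone. No model has a country term and no fit is split by country. The section adds that "by stratifying by patient, there is no need to adjust for time-invariant covariates such as age and sex".

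SAP section 9 reports no changes from planned analyses. The SAP document history says that some tertiary analyses were added, removed or updated, without naming country. SAP Amendment 1, now superseded, did take country into account in this section. The change log for Protocol Amendment 3 does not touch 9.7, so the by-country plan still stands in the protocol.

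**The concern.** An analysis that the protocol plans is missing from the SAP, and the section meant to list such changes does not list it. The protocol's rationale is that "the infectious aetiology of AECOPD has been suggested to vary according to geographical region", so a reader of 9.7 will expect to see whether the link between a pathogen and exacerbation differs among Hong Kong, the Philippines, Korea and Taiwan. A single pooled odds ratio cannot show that.

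The SAP's remark on time-invariant covariates is correct for confounding. It does not cover effect modification: a characteristic that is fixed within a patient can still change the size of the pathogen odds ratio, and country is such a characteristic. There is also a practical trap. Someone restoring the by-country element by adding country as a covariate would get nothing from it.

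Separately, a table titled in the protocol's terms but filled from the SAP's model would read in the opposite direction.

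**Working it through.** The plan states no figure for this analysis, so there is nothing to reproduce. Three checks were made.

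**1. Does a country main effect survive patient strata?** Let sample *j* of patient *i* have pathogen indicator x_ij, and let the patient have country indicator c_i. Write

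logit P(AECOPD) = α_i + β·x_ij + γ·c_i + δ·x_ij·c_i.

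Conditioning on the patient's number of AECOPD samples, m_i, the patient contributes

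exp{Σ over the AECOPD samples of (βx + γc + δxc)} ÷ Σ over all subsets of size m_i of the same expression.

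The term γ·c_i adds m_i·γ·c_i to the exponent in the numerator and in every denominator term, so it cancels. The term δ·x_ij·c_i varies with x_ij within the patient, so it stays.

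A numerical check used one simulated data set (200 patients split equally over 4 countries, 3 stable samples each, true odds ratios 1, 2, 2 and 4). The conditional log-likelihood was −200.686 at country coefficients of −5, 0 and +5: flat, hence not estimable. The pathogen-by-country terms were estimable, with odds ratios 0.70, 0.74, 2.12 and 4.12. Separate country fits gave 0.71, 0.74, 2.12 and 4.13.

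**2. Does the reversed direction matter?** Swapping the outcome in the same data gave log odds ratios of +0.4796 and −0.4796:

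exp(0.4796) = 1.616; exp(−0.4796) = 0.619; product = 1.000.

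The reversal is an exact reciprocal and loses no information.

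**3. How precise would country results be?** The assumptions, which are not in the documents, are the same layout with a true odds ratio of 2 everywhere, about 20% prevalence, a between-patient SD of 1 on the logit scale and a mean of 0.8 AECOPD samples per patient. Over 200 simulated data sets the median SE of the log odds ratio was 0.2505 pooled and 0.5042 for one country. The ratio of upper to lower 95% limit is exp(2 × 1.96 × SE):

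- pooled: exp(3.92 × 0.2505) = 2.67
- one country: exp(3.92 × 0.5042) = 7.22

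For an estimate of 2, the half-width factors are √2.67 = 1.63 and √7.22 = 2.69. The intervals are about 1.2 to 3.3 pooled and 0.74 to 5.4 for one country.

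Protocol 9.2 expects around 140 AECOPD samples from 200 enrolled, or 140/200 = 0.70 per patient. The assumed 0.8 is therefore slightly generous, and real intervals would be somewhat wider.

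**The case against.** The strongest reply is that little is lost. SAP 6.3.2 gives pathogen proportions with 95% CIs by country at stable and at AECOPD visits, and SAP 6.3.4.2 gives pathogen-associated AECOPD incidence by country. No tertiary objective in Protocol 2.3 or SAP 3.3 asks for a pathogen–exacerbation association, and SAP section 7 calls all analyses descriptive. The background in Protocol 1.1 contrasts Europe and the USA with Asia, so the rationale does not specifically call for comparing odds ratios among four Asian countries. Protocol 9.8 requires deviations to be described and justified in the final report in any case.

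Most of this stands, and it limits the importance of the point. It does not remove it. The retained proportions set separate stable and AECOPD figures side by side without matching patients to their own stable samples, and the incidence rates have no stable comparator. Neither is the within-patient odds ratio that 9.7 plans by country.

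Precision is also a fair objection. With a country SE of 0.504 and a true odds ratio of 2, z = ln 2 ÷ 0.504 = 1.38, and the 95% CI would exclude 1 only about 28% of the time. If one assumes six pathogens, four countries and three exposure definitions, there are 6 × 4 × 3 = 72 intervals, and about 72 × 0.05 = 3.6 would exclude 1 by chance. That argues for labelling the results exploratory and keeping the pooled estimate as the main one.

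**Conclusion.** The point holds as a modest mismatch between protocol and SAP: a planned by-country odds ratio is not produced, and the omission is not recorded in SAP section 9. That rests on the text alone. The figures on precision rest on the assumed layout above, in particular equal country sizes, which neither document states.

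Three stronger readings are tempting and are not supported.

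- **That the protocol's plan cannot be carried out because country cancels.** Only a main effect cancels, and neither document proposes one. Protocol 9.6 also asks for incidence by country, meaning country-specific estimates. Read the same way, 9.7 is estimable through separate fits or an interaction.
- **That regional differences go unanswered, or that the reversed odds contribute to this.** Proportions and incidence by country remain, and the reversal is a reciprocal unrelated to country.
- **That pooling will hide a real association.** In a simulation with a true odds ratio of 4 in one country and 1 in the other three, the pooled value was about 1.5 (0.9 to 2.5), against about 3.8 (1.4 to 10) in that country. This shows that dilution is possible, but the scenario is assumed and favourable to the argument. It does not predict this study's result.

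**What to change.** In SAP 6.4.4, keep the pooled odds ratio as the main estimate and always report it. For each selected pathogen, add as exploratory results either a pathogen-by-country interaction in the season-adjusted model or separate country fits. Do not add country as a main effect. Report country-specific odds ratios with 95% CIs and the number of informative patients per country, meaning those with both stable and AECOPD samples and with both positive and negative results. Mark a country as not estimable where there are none; do not substitute the pooled value.

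If country is to be left out instead, state this with reasons in SAP section 9.

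Use AECOPD versus stable as the direction in both documents. This is a wording alignment only.

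The cost is some SAP text and a few extra fits on data already collected; the SAP already fits an interaction of the same kind for season. The downside is wide country intervals, with limits differing by a factor of about 7 under the assumptions above. They should be presented as descriptive.

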9.8. Conduct of analyses

Any deviation(s) or change(s) from the original statistical plan outlined in this protocol will be described and justified in the final study report.

9.8.1. Sequence of analyses

- An interim analysis of the bacterial primary objective will be performed when at least 40 AECOPD sputum samples are available. The rate of positive samples will be computed for Hi, NTHi and Mcat together and per pathogen. No study report will be written at this stage.
- A final analysis of all objectives will be performed after the last subject last visit of the entire study. A final study report will be written at this stage.

9.8.2. Statistical considerations for interim analyses

All analyses are exploratory and will be conducted on final data and therefore no statistical adjustment for interim analyses is required.

10. ADMINISTRATIVE MATTERS

To comply with ICH GCP or other applicable guidelines, administrative obligations relating to data collection, monitoring, archiving data, audits, confidentiality, ownership, public disclosure requirements and publications must be met.

10.1. Electronic Case Report Form instructions

A validated GSK defined electronic data collection tool will be used as the method for data collection.

In all cases, subject initials will not be collected nor transmitted to GSK. Subject data necessary for analysis and reporting will be entered/transmitted into a validated database or data system. Clinical data management will be performed in accordance with applicable GSK standards and data cleaning procedures.

While completed eCRFs are reviewed by a GSK Biologicals' Site Monitor at the study site, omissions or inconsistencies detected by subsequent eCRF review may necessitate clarification or correction of omissions or inconsistencies with documentation and approval by the investigator or appropriately qualified designee. In all cases, the investigator remains accountable for the study data.

Once the database is archived and the clinical study report is complete and approved by all parties, each participating investigator will be provided with a CD-ROM of the final version of the data generated at his/her investigational site.

10.2. Study monitoring by GSK Biologicals

GSK will monitor the study to verify that, amongst other items, the:

- Data are authentic, accurate, and complete.
- Safety and rights of subjects are being protected.
- Study is conducted in accordance with the currently approved protocol, any other study agreements, GCP and all applicable regulatory requirements.

The investigator and the head of the medical institution (where applicable) agrees to allow the monitor direct access to all relevant documents.

The investigator must ensure provision of reasonable time, space and qualified personnel for monitoring visits.

Direct access to all study-site related and source data is mandatory for the purpose of monitoring review. The monitor will perform a eCRF review and a Source Document Verification (SDV). By SDV we understand verifying eCRF entries by comparing them with the source data that will be made available by the investigator for this purpose.

The Source Documentation Agreement Form describes the source data for the different data in the eCRF. This document should be completed and signed by the site monitor and

investigator and should be filed in the investigator's study file. Any data item for which the eCRF will serve as the source must be identified, agreed and documented in the source documentation agreement form.

Upon completion or premature discontinuation of the study, the monitor will conduct site closure activities with the investigator or site staff, as appropriate, in accordance with applicable regulations, GCP, and GSK procedures.

10.3. Record retention

Following closure of the study, the investigator must maintain all site study records (except for those required by local regulations to be maintained elsewhere) in a safe and secure location. The records must be easily accessible, when needed (e.g., audit or inspection), and must be available for review in conjunction with assessment of the facility, supporting systems, and staff. Where permitted by applicable laws/regulations or institutional policy, some or all of these records can be maintained in a validated format other than hard copy (e.g., microfiche, scanned, electronic); however, caution needs to be exercised before such action is taken. The investigator must ensure that all reproductions are legible and are a true and accurate copy of the original and meet accessibility and retrieval standards, including re-generating a hard copy, if required. Furthermore, the investigator must ensure that an acceptable back-up of the reproductions exists and that there is an acceptable quality control procedure in place for making these reproductions.

GSK will inform the investigator/institution of the time period for retaining these records to comply with all applicable regulatory requirements. The minimum retention time will meet the strictest standard applicable to a particular site, as dictated by ICH GCP or other applicable guidelines, any institutional requirements or applicable laws or regulations, or GSK standards/procedures otherwise, the minimum retention period will default to 25 years after completion of the study report.

The investigator/institution must notify GSK of any changes in the archival arrangements, including, but not limited to, archival at an off-site facility and transfer of ownership of the records in the event the investigator leaves the site.

